#### 6 STUDY TREATMENTS

#### 6.1 INVESTIGATIONAL PRODUCT DESCRIPTION

PRO 140 is a humanized IgG4, k monoclonal antibody (mAb) to the chemokine receptor CCR5. PRO 140 is provided at a concentration of 175 mg/mL and is intended for SC route of administration.

Kits will be labeled with a unique identification number. Each kit used during the Treatment Phase will contain two vials of PRO 140 or Placebo for SC injection. One milliliter (1 mL) of PRO 140 or placebo solution will be drawn from each vial and loaded into the syringe. A total of 350 mg (175 mg/mL) of PRO 140 or placebo is delivered as two 1 mL injections administered subcutaneously on opposite sides of the abdomen. One study injection kit will be assigned per subject per treatment visit.

Each vial of the PRO 140 product contains 1.4 mL antibody at 175 mg/ml in a buffer containing 5 mM L-histidine, 15.0 mM glycine, 95 mM sodium chloride, 0.3% (w/v) sorbitol, 0.005% (w/v) polysorbate 20 (Tween 20®), and sterile water for injection, at pH of 5.5.

Each vial of the Placebo contains 5mM Histidine, 15 mM Glycine, 95 mM Sodium Chloride, 0.3% (w/v) Sorbitol, 0.005% (w/v) Polysorbate 20 at a pH of 5.5.

**Note:** 1 mL injection will be drawn from 1.4 mL solution in a vial. Remaining 0.4 mL medication will be discarded appropriately from each vial.

Table 6-1 provides the unit strength, dosing frequency and mode of administration for the study drug.

[figure not shown]
Table 6-1: Investigational Product - PRO 140/Placebo at Treatment visits

Study Drug	Dosage Form	IP concentration	Dosing Frequency and Amount	Route of Administration
PRO 140	Parenteral solution	175 mg/mL	2 injections of PRO 140 (2 X 1 mL/inj.) on opposite sides of abdomen	SC injection
Placebo	Parenteral solution	0 mg/mL	2 injections of placebo (2 X 1 mL/inj.) on opposite sides of abdomen	SC injection

#### 6.2 INVESTIGATIONAL PRODUCT PACKAGING AND LABELING

The contents of each vial are described in section 6.1. PRO 140 and placebo kits will be labeled with information such as: study protocol #; fill volume; concentration; storage condition; a "use

CONFIDENTIAL Page 65 of 108

as per study protocol" statement; a cautionary statement; Sponsor's name and address; and the kit number.

Below are representative samples of the Investigational Product individual vial (Figure 6-1), syringe label (Figure 6-2), and kit labels (Figure 6-3) designated for use in this clinical protocol. Each kit contains two labeled vials and two syringe labels.

Figure 6-1: Investigational Product - Vial Label

Protocol: PRO 140_CD 03_GVHD Kit No. xx	Protocol: PRO 140_CD 03_GVHD Kit No. xxx
Subject No	Subject No
Single use 3 mL vial contains 1.4 mL of PRO 140 (175 mg/mL) or placebo solution for subcutaneous injection	Single use 3 mL vial contains 1.4 mL of PRO 140 (175 mg/mL) or placebo solution for subcutaneous injection
Store at 2°C to 8°C (36°F to 46°F)	Store at 2°C to 8°C (36°F to 46°F)
USE AS PER STUDY PROTOCOL	USE AS PER STUDY PROTOCOL
Caution: New Drug – Limited by Federal (or United Statute Law to Investigational Use	cs) Caution: New Drug – Limited by Federal (or United States) Law to Investigational Use
CytoDyn Inc., Vancouver, WA, USA	CytoDyn Inc., Vancouver, WA, USA

Figure 6-2: Investigational Product - Syringe Label

Protocol: PRO 140\_CD 03\_GVHD Contents of Kit No. xxx

This syringe contains 1 mL PRO 140 (175 mg/mL) or placebo solution for subcutaneous injection

USE AS PER STUDY PROTOCOL

Caution: New Drug – Limited by Federal (or United States) Law to Investigational Use

CytoDyn Inc., Vancouver, WA, USA

CONFIDENTIAL Page 66 of 108

Version 3.0 Date: 17 Jun 2016

## Figure 6-3: Investigational Product - Kit Label

Protocol: PRO 140_CD 03_GVHD	Kit No. xxx					
Site No	Subject No.					
This kit contains 2 single-use vials						
Each 3 mL vial contains 1.4 mL of PRO injection	O 140 (175 mg/mL) or placebo solution for subcutaneous					
Store at 2°C to 8°C (36°F to 46°F)						
USE AS PER STUDY PROTOCOL						
Caution: New Drug – Limited by Feder	ral (or United States) Law to Investigational Use					
CytoDyn Inc., Vancouver, WA, USA						

The study pharmacy manual provides the criteria regarding vial acceptance or rejection, as well as instructions for the preparation of the filled syringes to be used to administer drug.

#### **6.3** INVESTIGATIONAL PRODUCT STORAGE

Study drug will be shipped at 2°C to 8°C (refrigerated [36°F to 46°F]) to the study site. Upon receipt at the site, the responsible site staff or pharmacist should verify the integrity of the vials. Study drug should be stored at 2°C to 8°C (refrigerated [36°F to 46°F]). The contents of the vial should appear as a clear to opalescent, colorless to yellow solution. Possible presence of fine translucent particles is normal.

The site must maintain an accurate record of the shipment, storage, and dispensing of the study drug in a drug accountability log. An accurate record including the date and amount of study drug dispensed to each subject must be available for inspection at any time. A study CRA assigned to monitor the investigational site will review these documents once study drug has been received by the investigational site. Study drug will be accounted for on an ongoing basis during the study.

#### 6.4 INVESTIGATIONAL PRODUCT ADMINISTRATION

Guidelines for dose preparation can be found in the study pharmacy manual.

PRO 140 will be provided to the administering personnel in single-use syringes prepared from vials of study drug stored at 2-8°C at the site pharmacy prior to use. Each of two syringes is filled to deliver 1.0 mL of study drug.

Equivalent volumes of study drug will be administered subcutaneously on opposite sides of the abdomen.

CONFIDENTIAL Page 67 of 108

Date: 17 Jun 2016

A 25-guage needle should be used to remove IP from vial and for administration of IP to subjects. IP should be administered slowly over 15 seconds per mL.

Following each SC delivery of drug, careful examination will be made to assess the appearance of any study drug Injection Site Reactions (ISRs) as described in section 17.1.

All doses of study drug will be prepared by the credentialed pharmacist and will be administered as SC injection by a licensed medical professional (MD, DO, PA, LPN, LVN, NP, or RN).

Note: It is preferred that the same injection site be used throughout the study. At the same time, it is not recommended to inject the study drug into areas where skin shows signs of a previous injection site reaction(s). It is advised to change the injection site if any previous injection site reaction remains unresolved.

[figure not shown]
#### 6.5 INVESTIGATIONAL PRODUCT RECEIPT AND ACCOUNTABILITY

Study drug must be used in accordance with this protocol and only under the direction of the responsible investigator. The investigational site must maintain complete and accurate records showing receipt and disposition of all study drug, including master records listing the date of receipt, the number and nature of medication units received, and a dispensing record which includes each quantity dispensed, identification of the staff member to whom dispensed, the date of dispensing, the intended study participant, and the identification of the preparer. All used and unused study kits will be retained by the investigational site until drug accountability can be confirmed by study CRA during the monitoring visits. Instructions will be provided by Sponsor regarding final disposition of all study drug in compliance with applicable regulations.

#### 6.6 INVESTIGATIONAL PRODUCT DISPOSITION

All drug supplies are to be used only for this protocol and not for any other purpose. The investigator must not destroy any drug labels or any partially used or unused drug supply. At the conclusion of the study and as appropriate during the course of the study, the investigator will return all used and unused drug containers and drug labels to the drug distributor as directed by the Sponsor. A copy of the completed drug disposition form will be sent to the Sponsor or designee.

CONFIDENTIAL Page 68 of 108

## 7 DESCRIPTION OF PROTOCOL ASSESSMENTS AND PROCEDURES

#### 7.1 INFORMED CONSENT

Written informed consent will be obtained for this study by the Investigator or designee from all subjects before the performance of any protocol-specific procedure. This study will be conducted in accordance with the provisions of the Declaration of Helsinki.

In obtaining and documenting informed consent, the Investigator must comply with applicable regulatory requirements and must adhere to Good Clinical Practice (GCP). The Investigator, or designee, must fully inform subjects of all pertinent aspects of the study. Before informed consent may be obtained, the Investigator, or a person designated by the Investigator, must provide the subject ample time and opportunity to inquire about details of the study and to decide whether or not to participate in the trial. All questions about the trial must be answered to the satisfaction of the subject. Prior to the subject's participation in the trial, the written informed consent must be signed and personally dated by the subject and by the person who conducted the informed consent discussion. Authorization for release of protected health information must also be obtained, as per local policies.

#### 7.2 ASSESSMENT OF ELIGIBILITY

During the Screening Phase and at T1 Visit (prior to randomization), the Investigator must assess a subject's continued suitability and eligibility for the trial. The Inclusion and Exclusion criteria of this Protocol are described in sections 3.3.1 and 3.3.2. If the subject is not suitable or eligible for the trial then the subject will be a screen failure. Screen failure subjects may be re-entered into the study at a later time and re-screened.

## 7.2.1 Re-screening

If a subject initially fails to meet inclusion/exclusion criteria, and is later reconsidered for participation, the subject will be re-consented and assigned a new screening number at the time of re-screening. Subjects who fail their first screening attempt may be re-screened a maximum of once and may be enrolled if they are found to meet all inclusion and no exclusion criteria when re-screened.

#### 7.3 DEMOGRAPHIC INFORMATION

For the purposes of this study, demographic information will include:

- Date of birth
- Gender

CONFIDENTIAL Page 69 of 108

- Race (American Indian/Alaskan Native, Asian, Black/African American, Native Hawaiian/Pacific Islander, Caucasian, or other)
- Ethnicity (Hispanic/Latino or Not Hispanic/Latino)

### 7.4 MEDICAL HISTORY

A medical history will be recorded during the Screening Phase and will include:

- All ongoing medical conditions
- Baseline diagnosis requiring stem cell transplant, including AML or MDS
- Date of diagnosis
- Any prior medical conditions that have resolved within the last year

Events that emerge prior to the first treatment (T1) administration will be recorded in the medical history and not as AEs. Aside from being used to determine subject eligibility, this information will permit the Investigator to record the nature, duration and severity of any ongoing baseline medical conditions prior to the patient's receiving investigational product (IP) treatment.

Medical histories will be recorded using the body system categories outlined below:

	~ 1			
•	Card	iova	SCII	lar

Respiratory

• Gastrointestinal

Renal

• Hepatic

Neurological

• Endocrine

• Lymphatic

Hematologic

• Immunologic

Dermatologic

Psychiatric

[figure not shown]
Genitourinary

• Other

For each relevant history, the following will be documented:

- Disease/disorder/condition
- Date of onset/diagnosis
- History status (resolved or ongoing)
- Date of resolution, if applicable

CONFIDENTIAL Page 70 of 108

### 7.5 PRIOR / CONCOMITANT MEDICATIONS AND NON-STUDY TREATMENTS

A complete history of current therapies will be recorded in the source documents and on the appropriate page of the eCRF.

In addition to this, all other medications and therapies administered or taken by the subject beginning 30 days prior to Screening Visit and throughout the study will be recorded. Subjects must be questioned at each study visit concerning any new medications or changes in current medications including over-the-counter medication.

For each medication and non-study treatment, the following will be documented:

- Medication/treatment name (generic name may be used if trade name is unknown)
- Dose, unit, and frequency of dosing (individual dosages, not total daily dose).
  - Note: Each new dose of medication should be recorded as a separate entry, with the exception of medications that are given on a sliding scale. For these, it is acceptable to enter the range of the dosage, including the start and stop dates for which the specified dosage range was used.
- Route of dosing
- Indication for use
- The start date
- The stop date (if medication/therapy is not ongoing)

Please refer to Exclusion Criteria (section 3.3.2) for a list of prohibited treatments and/or procedures. All other medications that are appropriate for the care of the subject may be prescribed. If concomitant medications are started during the study, the indication for the concomitant medication should be recorded as an AE if it meets the criteria.

### 7.5.1 Excluded Medications and Therapies

Cyclophosphamide and CCR5 inhibitors other than PRO 140 (ex. maraviroc) are prohibited during this study.

[figure not shown]
# 7.5.2 Allowable Medications and Therapies

All other medications/therapies that are not otherwise prohibited and, in the judgment of the Investigator, are required for proper medical care of the subject may be prescribed.

#### 7.6 PHYSICAL EXAMINATION

The complete physical examination will include routine examinations for the following:

CONFIDENTIAL Page 71 of 108

- Head, Ears, Eyes, Nose, Throat (HEENT)
- Abnormalities of the extremities
- Neurologic abnormalities
- Heart/cardiovascular abnormalities
- Musculoskeletal abnormalities
- Dermatologic abnormalities
- Any other body system for which an abnormality is noted and which, in the opinion of the Investigator, is relevant to the safety of the subject or could impact safety or efficacy results for the subject; i.e., the abnormality is clinically significant (CS).

Each abnormality will be recorded and the Investigator will record an assessment of its clinical significance. After administration of the first dose of study treatment, each physical exam abnormality that is considered to be clinically significant will be recorded as an AE.

## 7.7 ELECTROCARDIOGRAM

12-lead ECG will be conducted and evaluated by the Investigator. The following parameters will be recorded: ventricular rate (beats per minute), PR interval (msec), QRS interval (msec), QT interval (msec), and QTc interval (msec). Additionally, the investigator will record the overall results of the ECG reading as either normal or abnormal, and as either not clinically significant or clinically significant. If abnormalities are observed, each will be recorded. Each treatment-emergent abnormality that is considered to be clinically significant will be recorded as an AE. Each ECG should be signed by a physician.

### 7.8 HUMAN IMMUNODEFICIENCY VIRUS (HIV) RAPID ANTIGEN TEST

Test should be performed per the site standard kits and procedures. The result reports will need to be reviewed and signed by the Investigator.

[figure not shown]
### 7.9 VITAL SIGNS, HEIGHT AND WEIGHT

Vital signs collected during the Treatment Phase will be performed post-treatment, assessed within 15 minutes following study treatment administration. Height and weight will be assessed only at Screening and unscheduled visits.

The following will be collected:

• Height and weight; BMI will be calculated using high and weight measurements

CONFIDENTIAL Page 72 of 108

- Systolic and diastolic blood pressure (taken after the subject has been seated for at least 5 minutes)
- Heart Rate (HR)
- Respiration Rate (RR)
- Temperature

## 7.10 EASTERN COOPERATIVE ONCOLOGY GROUP (ECOG) PERFORMANCE STATUS

ECOG performance status test is used to evaluate the patients' level of functioning per Table 7-1 below:

Table 7-1: ECOG Performance Status

GRADE	ECOG PERFORMANCE STATUS
0	Fully active, able to carry on all pre-disease performance without restriction
1	Restricted in physically strenuous activity but ambulatory and able to carry out work of a light or sedentary nature, e.g., light house work, office work
2	Ambulatory and capable of all selfcare but unable to carry out any work activities; up and about more than 50% of waking hours
3	Capable of only limited selfcare; confined to bed or chair more than 50% of waking hours
4	Completely disabled; cannot carry on any selfcare; totally confined to bed or chair
5	Dead

[figure not shown]
#### 7.11 CLINICAL LABORATORY ASSESSMENTS

Blood and urine samples will be collected according to the time points in the schedule of assessments for analysis of the following parameters:

#### 7.11.1 Routine CBC

- Includes hemoglobin, hematocrit (HCT), red blood cell (RBC) count, white blood cell (WBC) count, WBC differential count (%), absolute neutrophils count (ANC) and platelets count.
  - Note: Platelet recovery will be defined as post-transplant increase in platelet levels to greater than 20,000/µL on two consecutive counts at least 2 days apart, if no platelet transfusion is given on or between the days of the two counts and the second platelet count is at least as high as the first. The date of platelet recovery will be defined as the day of the first eligible count per above. Neutrophil

CONFIDENTIAL Page 73 of 108

recovery will be defined as an increase in absolute neutrophil count (ANC) to greater than  $500/\mu$ L on 2 consecutive days. The date of neutrophil recovery will be defined as the day of the first count above the threshold.

## 7.11.2 Biochemistry

• Biochemistry profile includes assessment of:

Hepatic function indicators: total and direct bilirubin, alkaline phosphatase (ALP), aspartate aminotransferase (AST), alanine aminotransferase (ALT), total protein, Lactate dehydrogenase (LDH)

Renal function indicators: Blood Urea Nitrogen (BUN), creatinine

Electrolytes: sodium, potassium, chloride, calcium and bicarbonate

Other: glucose (random), cholesterol (total)

## 7.11.3 Population Pharmacokinetics

• Blood samples will be collected and evaluated per the study schedule of assessments.

## 7.11.4 Lymphocyte phenotype panel

• Lymphocyte phenotype panel will be performed and evaluated per the study schedule of assessments.

## 7.11.5 T-cell and Myeloid chimerism evaluation

• T-cell and myeloid chimerism tests will be evaluated per the institutional standards.

## 7.11.6 Anti-idiotypic antibodies to PRO 140

• The first samples for anti-idiotypic antibodies for PRO 140 may be collected at the T1 prior to first dose of PRO 140

\*Note: Sera will be collected from study subjects and stored at  $-80^{\circ}$ C for future analysis.

## 7.11.7 Serum pregnancy test

• Only for female subjects of childbearing potential. Childbearing potential is defined as someone who is not surgically sterile or is not more than one year past complete cessation of menstrual cycles.

#### 7.11.8 Urinalysis

• Urine samples will be tested for color, appearance, specific gravity, pH, protein, glucose, occult blood, ketones, RBC, WBC, epithelial cells, bacteria, casts, crystals

CONFIDENTIAL Page 74 of 108

Date: 17 Jun 2016

All laboratory reports will be reviewed by the Investigator.

Post-treatment abnormal results that are considered by the Investigator to be clinically significant will be recorded as adverse events. If the Investigator judges it necessary, testing may be repeated in order to make the determination of clinical significance. Validated, quality-controlled laboratory data will be transferred to the main database for analyses.

#### 7.12 RANDOMIZATION

Subjects who are eligible to participate in the trial will be randomized to one of the treatment groups via IWRS (Interactive Web Based Randomization System) at the T1 Visit prior to IP administration. The randomization will be central and will use mixed block size of 2 and 4 with a 1:1 ratio of Active Treatment to Control Treatment to ensure even distribution of Active and Control subjects. A randomization plan that details the stratification and randomization will be developed.

#### 7.13 PRO 140 ADMINISTRATION

PRO 140 will be administered -2/-3 days before the stem cell infusion, on the day of stem cell infusion (Day 0) and thereafter on days 7, 14, 21, 28, 42, 56, 70, 84 and 98 as per the study schedule of assessments (Table 4-1).

Refer to section 6.4 for details on the procedure of PRO 140 administration.

#### 7.14 STANDARD OF CARE

For the purpose of this study, the combination regimen of tacrolimus plus methotrextate per below will be considered as standard of care (Ratanatharathorn et al., 1998 and Ruutu et al., 2014):

- For tacrolimus the starting dose of 0.02-0.03 mg/kg/day will be initiated on day -1 of transplant by continuous IV infusion to target whole blood levels of tacrolimus between 5 and 10 ng/ml. The route of administration will be converted from IV to oral at the ratio of 1:3 to 1:4 when patients are able to tolerate oral intake. When a patient is switched from IV to oral tacrolimus, the target for blood levels of tacrolimus will be kept at approximately 10 ng/ml. For dose modifications institutional standards will be followed.
- For methotrexate the initial dose will be a minimum of 5 mg/m^2 on day +1 after the transplant. Three additional doses of minimum 5 mg/m^2 are given on days +3, +6 and +11 after the transplant. The day +11 dose is omitted in case of any toxicity of grade II or higher. The drug is given as bolus IV injection. For dose modifications institutional standards will be followed.

CONFIDENTIAL Page 75 of 108

[figure not shown]
#### 7.15 INJECTION SITE REACTION ASSESSMENT

At each visit during the Treatment Phase, an injection site reaction assessment will be made for the current and previous injection sites. Injection site reaction assessments are recorded by the Investigator starting after the first injection is given. Refer to sections 9.1.8 and 17.1 for more details.

## 7.16 PAIN ASSESSMENT USING VISUAL ANALOG SCALE (VAS)

Tolerability of repeated subcutaneous administration of PRO 140 is evaluated based on assessment of subject-perceived injection site pain using the Pain Visual Analog Scale (VAS). Subjects will be asked to mark the point that best represents the average pain intensity at the injection site over the past week on a horizontal line (100 mm in length) anchored by the following word descriptors at each end, "no pain" on the left side and "pain as bad as it could possibly be" on the right side of the line. The subject marks on the line or by pointing to a position on the line the point that they feel represents their perception of their pain state. The VAS score is determined by measuring in millimeters from the left-hand end of the line to the point that the patient marks. The first VAS assessment will occur prior to study treatment administration at visit T2.

Figure 7-1: Sample Visual Analog Scale

CONFIDENTIAL Page 76 of 108

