### 4 STUDY SCHEDULE

This research study is divided into three study phases:

- (1) Screening Phase (Screening to T1 Visit) begins with signing of Informed Consent and lasts up to 4 weeks (28 days).
- (2) Treatment Phase (up to 14 weeks ± allowed windows). Eligible subjects will be randomized and receive up to 11 study treatments (PRO 140 or placebo), given on Day -3 or Day -2 prior to stem cell infusion, on the day of stem cell infusion (Day 0), and then weekly for 30 days (at Week 1, Week 2, Week 3 and Week 4) after which it will be administered every two weeks for up to 98 days (at Week 6, Week 8, Week 10, Week 12 and Week 14).
- (3) Follow-Up Phase (up to one year). Subjects who have completed the Treatment phase or who have withdrawn from the study will be followed-up at 2 weeks after the last treatment visit and one year after first treatment visit.

Procedures to be performed during each of these study phases are described below and provided as a Schedule of Assessments in Table 4-1.

CONFIDENTIAL Page 54 of 108

Table 4-1: Schedule of Assessments

iis	iV bəlub	əųəsu	n						×	×	×	×		×	×				
p Phase le year)	Follow-up Visit 2	52	Day 365±14							×						X			
Follow-Up Phase (up to one year)	Follow-up Visit 1	16	Day 112±3							X	X		X	×	X	X			
	T11	14	Day 98±3						×	×	×		X	×	X		X	×	X
	T10	12	Day 84±3							×				×	X	X			
	T9	01	Day 70±3							×	×		X	×	X				
	T8	œ	Day 56±3						X	X				×	X	X			
Phase	T7	9	Day 42±3							X	X			×	X		X	X	X
Treatment Phase (14 weeks)	9L	4	Day 28±3							X			X	×	X	X			
Tre	TS	e	Day 21±3											X					
	T4	2	Day 14±3							×	×			×	Х				
	T3	-	Day 7±3											×					
	T2		Day 0						×	×				×					
	T.1		Day -3/- 2			×	×			×	×		X	×	X	X			[6]X
Screening Phase (up to 4 weeks)	Screening Visit	Up to -4 weeks	Up to -28 days		×	×	×	×	×	×	×	X	X	×	X	X	X	×	
				Protocol Section	Section 7.1	Section 7.2	Section 7.4	Section 7.3	Section 7.6	Section 7.9	Section 7.10	Section 7.9	Section 7.7	Section 7.11.1	Section 7.11.2	Section 7.11.3	Section 7.11.8	Section 7.11.7	Section 7.11.6
Study Phase	Visit	Weeks	Days	Procedures	Informed Consent 	Eligibility Evaluation 	Medical History 	Subject Demographic	Physical Examination	Vital Signs 	ECOG performance score	Height and Weight	ECG	Complete Blood Count (CBC) 	Serum Biochemistry 	ЬРК	Urinalysis 	Serum Pregnancy Test 	Anti-idiotypic antibodies to PRO 140

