- ONLY for women of childbearing potential Urine samples will be tested for color, appearance, specific gravity, pH, protein, glucose, occult blood, ketones, RBC, WBC, epithelial cells, bacteria, casts, crystals Anti-idiotypic antibodies to PRO 140 at visit T1 to be performed prior to dosing
- For GVHD diagnosis and grading refer to sections 7.17 and 7.18 After PRO 140 or Placebo dosing
- [7] [8] [9] [11] [12]
- Injection Site Pain Assessment (VAS) will be performed prior to study treatment administration beginning at visit T2 (to assess the average pain felt at the injection site since the last injection)

Page 57 of 108 CONFIDENTIAL

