### **Post-Treatment**

- Injection Site Reaction Assessment (see section 7.15)
  - ➤ **Note:** To assess injection site reactions, refer to the investigator injection site reaction table (refer to section 17.1).
- Injection Site Pain Assessment (VAS) (section 7.16)
- Vital Signs (see section 7.9) will be assessed within 15 minutes of study treatment administration.
- Assessment of Adverse Events (AE) (see section 9)

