## **8.2.3** Safety Assessments

- Tolerability of repeated subcutaneous administration of PRO 140 as assessed by study participants (using Visual Analogue Scale) and by investigator-evaluation of injection site reactions
- Frequency of treatment emergent adverse events and serious adverse events

CONFIDENTIAL Page 80 of 108

- AML or MDS relapse rate by Day-100
- Changes and shifts in laboratory measurements over time
- Changes in Electrocardiogram (ECG) parameters over time

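### The injection-pain VAS has two conflicting recall periods, and the one-week recall in section 7.16 leaves out the first 7 days after injection at 5 of 10 assessments (T7-T11, nominal days)

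*Protocol*

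**What the plan says.** **Recall period.** Protocol section 7.16 has the subject mark "average pain intensity at the injection site over the past week" on a 100 mm line. Footnote 12 to Table 4-1 instead gives the purpose as "to assess the average pain felt at the injection site since the last injection". The SAP repeats that footnote in its Appendix 1. Both wordings are current text.

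**Timing.** Section 7.16 states: "The first VAS assessment will occur prior to study treatment administration at visit T2". Footnote 12 likewise places the VAS before dosing from T2 onward, and both schedules show no VAS at T1. Section 4.2.1, however, lists a VAS under its post-treatment assessments at T1. Sections 4.2.2 and 4.2.3 list it after study drug administration, though there only the order of the list suggests the timing.

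**Dosing.** Section 7.13 gives the first injection 2 or 3 days before the transplant, the second on Day 0, and "thereafter on days 7, 14, 21, 28, 42, 56, 70, 84 and 98". Section 4 describes the later part as "after which it will be administered every two weeks for up to 98 days". Table 4-1 allows ±3 days at T3 to T11.

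**Use.** Section 8.2.3 includes the VAS in a safety assessment: "Tolerability of repeated subcutaneous administration of PRO 140 as assessed by study participants (using Visual Analogue Scale"), paired in the same item with the investigator's evaluation of injection sites. SAP section 8.4.2 plans n, mean, SD, minimum and maximum. It names no recall period and does not say whether the summary is by visit.

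**The concern.** A pre-dose VAS always looks back at the previous injection. While injections are a week apart, the two recall periods coincide. Once they are two weeks apart, a one-week recall covers only the second week after the injection, so pain felt soon after it is not rated.

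The dosing interval changes between T6 and T7, and so does the part of the post-injection period that is rated. Someone reading mean VAS over time could take a fall at that point as growing tolerance of repeated injections when the question had simply stopped covering the early days. A recall period cannot be corrected after the data have been collected.

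**Working it through.** The documents give no figure to reproduce. The check is date arithmetic.

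**Inputs**
- Dosing days: -3 or -2, 0, 7, 14, 21, 28, 42, 56, 70, 84, 98 (protocol section 7.13).
- VAS before dosing at T2 to T11, so 10 scheduled assessments (section 7.16; Table 4-1 and footnote 12).
- Recall: 7 days (section 7.16) or back to the previous injection (footnote 12).
- Visit windows: ±3 days at T3 to T11, none at T2 (Table 4-1).

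**Formulas**
- Interval = day of this visit minus day of the previous injection.
- Days unrated under section 7.16 = max(0, interval - 7).
- Shortest and longest intervals put the two visits at opposite ends of their windows. For T7: shortest (42 - 3) - (28 + 3) = 8 days; longest (42 + 3) - (28 - 3) = 20 days.

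| Visit | Nominal interval (days) | Unrated, nominal | Interval with windows | Unrated with windows |
|---|---|---|---|---|
| T2 | 2-3 | 0 | 2-3 | 0 |
| T3 | 7 | 0 | 4-10 | 0-3 |
| T4-T6 | 7 | 0 | 1-13 | 0-6 |
| T7-T11 | 14 | 7 | 8-20 | 1-13 |

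On nominal days the one-week recall misses the first 7 days after injection at T7, T8, T9, T10 and T11, which is 5 of 10 assessments. With recall back to the previous injection, the unrated days are 0 at all 10.

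**T2.** A one-week recall reaches 7 - 3 = 4 or 7 - 2 = 5 days before the first injection. No injection site exists in those days, so they hold no injection pain, and T2 is not counted as a substantive difference.

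**Does the schedules' wording make all visits comparable?** Suppose, for illustration, that pain has constant level x, lasts d days with d no more than 7, and is averaged exactly over the recall period, on nominal days:
- T3-T6, either wording: x·d/7.
- T7-T11, section 7.16 wording: 0.
- T7-T11, footnote 12 wording: x·d/14, half the T3-T6 value.

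The schedules' wording closes the gap in coverage. The same pain still gives a lower average over 14 days than over 7, so weekly and two-weekly visits should not be pooled or read as one series.

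**The case against.** **Points that stand.** SAP section 8.4 plans no inferential statistics for safety data, and no trend analysis of the VAS is planned. Both arms share one schedule and receive the same number and volume of injections, so the recall gap does not favour either arm; at most it makes a real difference at T7 to T11 harder to see. Early pain can be recorded by other routes: the investigator examines present and earlier injection sites at each treatment visit (section 7.15), Appendix I grades injection-site pain, and adverse events are elicited by direct questioning with onset and end dates (sections 9.1 and 9.1.1). These do not replace the subject's own rating, which the protocol lists as a separate component, but they limit what is lost.

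**Stronger readings that the documents do not support**
- *The definitions differ at 6 of 10 assessments.* This counts T2, where the extra days precede any injection.
- *A reaction that resolves within a week always scores 0 at T7 to T11.* This is true on nominal days only. With an 8-day interval, just 1 day is unrated.
- *Scores will fall at T7.* No section gives a time course for injection pain. The nearest is section 1.4.3.6, which describes reactions in an earlier HIV study as mild and short-lived. The fall is possible, not established.
- *Sites will use different recall periods.* What subjects see depends on the form. The images of the scale (protocol Figure 7-1, SAP Figure 8-1) were not available for this check, so what they print is unknown.

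**Conclusion.** The inconsistency is real and unreconciled. Followed as written, section 7.16 gives a subject-reported tolerability score that omits the first 7 days after injection at 5 of 10 assessments on nominal days, and 1 to 13 days at those visits across the allowed windows. This part rests only on the stated dosing days and the pre-dose timing.

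The further conclusion, that T7 to T11 could understate pain and that a T6-to-T7 drop could be an artefact of recall, also requires injection pain to be short-lived. That is plausible but assumed.

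The point is minor. It concerns one descriptive safety measure, does not touch the primary endpoint, and gives no reason to expect bias between arms. It is still worth correcting, because the change is only to wording.

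**What to change.** 1. In section 7.16 and on the form, replace the one-week recall with recall back to the previous injection, as both schedules already have it.
2. Reconcile the visit lists with the pre-dose rule starting at T2: remove the post-dose VAS at T1 from section 4.2.1, and place the VAS before study drug administration in sections 4.2.2 and 4.2.3.
3. In SAP section 8.4.2, state the recall period and summarise the VAS by visit, or in three groups by dosing interval: T2 (2-3 days), T3-T6 (7 days) and T7-T11 (14 days). Do not interpret a change between groups as a change in tolerance.
4. If forms have already been used, establish which recall period they printed. If it was one week, report T7-T11 with the coverage gap stated.

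The cost is the wording of one question, a few lines in the visit lists and a sentence or two in the SAP. No visit, procedure or dose changes. Averages over 7 and 14 days will still not be directly comparable, which is why item 3 is needed as well as item 1.
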